### **11.0 Statistical/Data Analysis Plan**

#### **11.1 Statistical Considerations:**

List the statistical methods to be used to address the primary and secondary objectives, specific aims, and/or research hypotheses. Explain how missing data and outliers will be handled in the analysis. The analysis plan should be consistent with the study objectives. Include any sub-group analyses (e.g., gender or age group). Specify statistical methods and variables for each analysis. Describe how confounding variables will be controlled in the data analysis

The primary outcome will be the difference in VAS from baseline to 30 minutes and from baseline to 60 minutes. Our research hypothesis is that the measured pain relief using 15mg of intramuscular ketorolac will be non-inferior to the measured pain relief using 60mg of intramuscular ketorolac. Whereas in a clinical study where the research hypothesis is that one treatment, say drug A, is demonstrated to have a better (improved pain relief) outcome than the second treatment, say drug B, we are hypothesizing that smaller dose drug is not inferior in terms of pain relief than the higher drug dose. We fully suspect that the higher drug dose will have a better average outcome, but the question of interest is, is the outcome for the lower dose drug non-inferior to that of the higher drug dose. The analysis used in this study is a non-inferiority test. This hypothesis can be tested using a variety of methods that involve the construction of one-sided confidence interval or one-sided, two-sample equal-variance t-test with alpha of 0.05. In both methods, the power and sample size can be computed.

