### **Primary Outcome Variable Data:**

The primary outcomes will be a clinically significant reduction in the numeric rating using the visual analog scale at 30 and 60 minutes from medication administration and compared to the pre-treatment VAS.

The primary outcome variables will be the change in subjective pain reported by patients using a VAS. The VAS is a validated measurement instrument used to record subjective reports of pain, or other subjective conditions. There are several different VAS constructs but this study will utilize a single horizontal line measuring 0-100 mm with short vertical marks as borders at each edge. All investigators will independently measure the VAS line to ensure that the printed line on the VAS form measures exactly 100 mm. The phrase "No pain" will be placed to the left of the 0 mm mark and the phrase "Severe Pain" will be placed to the right of the 100 mm mark. There will be no numerical or other incremental marks along, within or above the scale. The study subject will be instructed on the use of the scale prior to having their pain assessed. They will be informed that the scale measures from left to right, least to greatest level of pain. To annotate their pain level, they will be instructed to signify their level of pain on a scale of "0 mm or no pain at all" to "100 mm or Severe Pain" by making a single vertical mark through the horizontal VAS line on the document. If they do not make a vertical mark (circle, forward slash, backward slash, or otherwise), it is not through the horizontal VAS line, or illegible the investigator will retrain the patient on how to complete the form and a new form will be provided for the patient. An extra VAS is included in each Subject Study Packet for this purpose. Once completed, the forms will be returned to the subject study packet.

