#### **11.2 Sample Size:**

n=122 (This assumes 10% dropouts or withdrawals from our required n=110)

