**11.5 Please provide a justification for your sample size**

In this study, we assume that we are comparing the mean VAS between the 2 Groups, and the margin of non-inferiority is -13 mm. The actual difference between the means is assumed to be 0 and the standard deviation is assumed to be 27 for the 2 Groups (estimated from the Motov manuscript). Group sample sizes of 55 and 55 achieve 80% power to detect non-inferiority using a one-sided, two-sample equal-variance t-test with alpha of 0.05. The sample size per arm was increased from 55 to 61 to account for an anticipated 10% dropout or withdrawal of subjects (5.5 subjects was rounded to 6 subjects).

**11.6 Data Analysis Plan: Complete description: Background, Objectives, Design, Step by Step how the project is going to be done, Data analysis plan:**

To test for non-inferiority of dose 15mg to dose 60 mg using the VAS pain score, the analysis to be used is called an interval test. The hypothesis will be tested using the construction of one-sided confidence intervals or one-sided, two-sample equal-variance t-test with alpha of 0.05. To test that the lower dose has less adverse effects, we will use the one-sided z-test for testing two independent proportions. All tests will be conducted at the 0.05 level of significance.

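### VAS change at 30 and at 60 minutes are both primary with no rule for combining them, and the stated 80% power describes one time point only

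*Protocol*

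**What the plan says.** Protocol section 10.2 opens in the plural: "The primary outcomes will be a clinically significant reduction in the numeric rating using the visual analog scale at 30 and 60 minutes". Its next paragraph puts the outcome as a change: "The primary outcome variables will be the change in subjective pain reported by patients using a VAS". Section 11.1 again names both time points: "The primary outcome will be the difference in VAS from baseline to 30 minutes and from baseline to 60 minutes".

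Section 11.5 sizes one comparison and names no time point: "we assume that we are comparing the mean VAS between the 2 Groups, and the margin of non-inferiority is -13 mm". It adds "The actual difference between the means is assumed to be 0", takes an SD of 27 in both groups, and concludes: "Group sample sizes of 55 and 55 achieve 80% power to detect non-inferiority using a one-sided, two-sample equal-variance t-test with alpha of 0.05". Enrolment is then raised to 61 per arm for 10% dropout. Section 11.1, by contrast, says that the team expects the higher dose to do better on average.

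On error control, section 11.6 says only: "All tests will be conducted at the 0.05 level of significance". The SAP assigns an independent-samples t-test to the primary outcome. It gives no time point, no order of testing and no rule for two results.

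**The concern.** Two primary comparisons can be turned into one conclusion in three ways: both must succeed, either is enough, or one is named as primary and the other is supportive. Each has its own power and its own error rate, and the plan does not choose among them.

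Two things are at stake. First, the trial could show non-inferiority at one time point and miss it at the other, and the documents do not say what would then be concluded. Second, a reader will take 80% as the chance that the trial supports its overall claim. Because the two time points are joined by *and*, the natural reading is that both are required, and 80% is not the power of that claim. If the rule is left open and success at either time point is accepted once the results are known, the 5% error rate no longer holds.

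**Working it through.** **Inputs from section 11.5:** margin 13 mm, SD 27 mm, true difference 0, one-sided alpha 0.05, 55 evaluable per arm (61 enrolled).

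**Assumptions, not in the documents:** 27 is the SD of change; SD, margin and true difference are the same at both times; the 30- and 60-minute changes correlate at ρ = 0.5 to 0.9.

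**1. The plan's own figure.** The standard error is SD × √(2/n) = 27 × √(2/55) = 5.149 mm. The noncentrality is 13/5.149 = 2.525, and the critical t on 108 df is 1.659. Power from the noncentral t is **80.6%**. At 54 per arm it is 79.98%, so 55 is the smallest n that reaches 80%. At 61 per arm the standard error is 4.889, the noncentrality 2.659, and power 84.1%.

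**2. Both required.** Let k be the normal quantile of the single-comparison power: 0.864 at 55 and 0.999 at 61. Joint power is the bivariate normal probability Φ₂(k, k; ρ). Simulating 400,000 draws of two correlated t statistics gives the same values.

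**3. Split result.** The chance that exactly one time point succeeds is 2 × (single power − joint power). At ρ = 0.5 this is 2 × (80.6 − 69.6) = 22%.

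**4. Either accepted later.** With both true differences exactly at the margin, the chance of a false non-inferiority claim is 1 − Φ₂(1.645, 1.645; ρ).

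| ρ | Both, 55/arm | Both, 61/arm | Exactly one, 55/arm | Error if either suffices |
|---|---|---|---|---|
| 0.5 | 69.6% | 74.5% | 22% | 8.8% |
| 0.7 | 72.1% | 76.6% | 17% | 8.0% |
| 0.9 | 75.7% | 79.8% | 10% | 6.8% |

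At ρ = 0.95, joint power is 77.2% at 55 per arm and 81.1% at 61.

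**5. If 27 is the SD of raw scores.** With equal SDs and baseline/follow-up correlation r, the SD of change is 27 × √(2(1 − r)), which is 31.9 at r = 0.3 and 20.9 at r = 0.7. At 55 per arm, single-time-point power is then 68% or 94%. Joint power is about 54–62% or 90–92%.

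**6. Adjusting for baseline VAS.** If 27 is the SD of change and raw SDs are equal, the residual SD is 27 × √((1 + r)/2). Joint power uses the residual correlation implied by ρ = 0.5 to 0.9. At 55 per arm (107 df):

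| r | Residual SD | One time point | Both |
|---|---|---|---|
| 0.3 | 21.8 | 92.9% | 86.8–89.9% |
| 0.5 | 23.4 | 89.5% | 81.5–85.7% |
| 0.7 | 24.9 | 85.9% | 76.4–81.6% |

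The last row implies a raw SD of 27/√(2 × 0.3) = 34.9 mm. That is hard to square with an entry threshold of 20 mm: even a uniform spread from 20 to 100 has an SD of 80/√12 = 23.1. The row is shown as the least favourable case.

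**The case against.** The strongest reply is that 70–76% is one scenario. It needs a both-required rule that the documents never state, a correlation they never give, and 27 being the SD of change. Section 11.5 speaks of mean VAS and does not settle the last point; step 5 shows that if 27 is the raw-score SD, joint power could lie well below or well above 80%. This stands. The size of the shortfall is therefore conditional, and the SD must be identified before any new power figure is written into the protocol. It does not touch the missing rule or the undefined split result.

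Two further replies have force. A zero difference is an ordinary planning assumption, and the sentence in 11.1 about the higher dose is there to explain why non-inferiority is the question. This is a matter for reconciliation and does not show that the sample size is wrong. A reader might take the emergency department trial cited in section 9.2 as settling the matter in favour of zero, but it compared intravenous doses of 10, 15 and 30 mg within 30 minutes, and so covers neither the 60 mg intramuscular dose nor the 60-minute time point.

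Baseline adjustment is also a precision gain and does not itself supply the missing rule. It is worth including because the baseline VAS is already collected.

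The opening sentence of 10.2 might be read as a responder endpoint. The paragraph after it and section 11.1 both point to change in VAS, so only consistent wording is needed.

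**Conclusion.** The concern holds. Two time points are primary, no rule combines them, and the stated 80% is correct for one comparison only. If both are required, power is about 70–76% at the planned 55 evaluable per arm, under the three assumptions listed in the working. If one time point is named as primary, the 80% stands as written.

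Three stronger readings are not supported:

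- **That type I error is inflated as planned.** Requiring both keeps it at or below 5%. The 7–9% arises only if either success were accepted, with both differences at the margin, and the documents do not propose that rule.
- **That power is below 80% whatever happens.** With all 61 per arm evaluable it is about 75–80%, and it passes 80% at a correlation of 0.95.
- **That no part of the study is masked, so the rule can no longer be fixed cleanly.** Study numbers do show the dose, but section 9.4 describes a single-blinded trial and section 10.2 defers VAS measurement until data collection ends. What matters is whether results by arm have been seen.

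**What to change.** 1. In section 11.1 and the SAP, state one rule: either one named primary time point with the other as key secondary, or both required at one-sided 0.05. Date it before any results by arm are seen. A recorded date is needed because section 10.2 defers VAS measurement while section 10.14 has data transcribed daily, and because the SAP describes one choice of analysis as made during analysis. If results by arm have already been seen, use the both-required rule, which cannot raise the type I error.
2. In section 11.5, refer to mean VAS change and state whether the SD of 27 is for change or for raw scores. Then restate the power for the chosen rule, with the correlation shown as an assumption and enrolment unchanged.
3. Reconcile the expectation in 11.1 that the higher dose does better with the zero difference assumed in 11.5.
4. Analyse each time point by ANCOVA with baseline VAS as covariate, and compare the one-sided 95% bound with 13 mm. If analysis has begun, report this as a sensitivity analysis beside the planned t-test.

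The cost is wording in two documents and one regression per time point in SPSS, with no extra patients or data. The drawback is a less favourable power statement if both are required. For information, restoring 80% under that rule with the t-test would take about 62–69 evaluable per arm (ρ = 0.9 to 0.5), before dropout; the fix does not ask for this.

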#### **11.2 Sample Size:**

n=122 (This assumes 10% dropouts or withdrawals from our required n=110)

**11.3 Total number of subjects requested (including records and specimens):**

122

**11.4 If you are recruiting by study arm, please identify the arms of the study and how many subjects will be enrolled in each arm**

15mg IM ketorolac arm = 61 subjects  
60mg IM ketorolac arm = 61 subjects

**11.5 Please provide a justification for your sample size**

In this study, we assume that we are comparing the mean VAS between the 2 Groups, and the margin of non-inferiority is -13 mm. The actual difference between the means is assumed to be 0 and the standard deviation is assumed to be 27 for the 2 Groups (estimated from the Motov manuscript). Group sample sizes of 55 and 55 achieve 80% power to detect non-inferiority using a one-sided, two-sample equal-variance t-test with alpha of 0.05. The sample size per arm was increased from 55 to 61 to account for an anticipated 10% dropout or withdrawal of subjects (5.5 subjects was rounded to 6 subjects).

**11.6 Data Analysis Plan: Complete description: Background, Objectives, Design, Step by Step how the project is going to be done, Data analysis plan:**

To test for non-inferiority of dose 15mg to dose 60 mg using the VAS pain score, the analysis to be used is called an interval test. The hypothesis will be tested using the construction of one-sided confidence intervals or one-sided, two-sample equal-variance t-test with alpha of 0.05. To test that the lower dose has less adverse effects, we will use the one-sided z-test for testing two independent proportions. All tests will be conducted at the 0.05 level of significance.

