To measure the subject's reported level of pain on the VAS, the investigator will measure from the beginning of the scale to the vertical mark drawn by the subject. The "0 mark" on the metric tape measure will be aligned with the "0 mark" on the VAS form and the millimeters from the "0 mark" to the vertical line representing the subject's pain will be tallied. This distance will be annotated next to the scale for ease of reference. All VAS measurements will be completed and documented in the same manner for the 30 and 60 minute intervals. This study will use a previously validated measure of a 13 mm change in VAS to determine the minimum clinical significant difference (MCSD). (REF). Please refer to the statistical analysis portion of this document for more information about how this data will be used.

VAS measurements will not be taken during the data collection phase of this study. Only after data collection has been completed for the entire study and all VAS forms have been completed for all study subjects will the investigators actually measure and record the VAS scores. The purpose of not measuring the VAS at the time of data collection is to reduce research bias. Measurement of all VAS forms will take place at a predetermined time and place for both investigators (PI and AI). During the VAS measurement process, all investigators involved with the research must agree upon the measurement obtained. If, there is a discrepancy with the measurement process or measurement obtained, the VAS will not be used and the patient will be excluded from the study. The methodology for measuring the VAS will be based on prior literature explaining the process, in order to reduce inaccuracies 26.

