Cover Page

Title: Comparison of Intramuscular Ketorolac at Two Single-Dose Regimens for Treatment of Acute Musculoskeletal Pain in a Military Emergency Department: A Randomized Controlled Non-Inferiority Trial

NCT: Not received yet

Date: 2/5/2021

Statistical Analysis Plan

Data analysis will be performed using the statistical software SPSS (IBM SPSS Statistics for Windows, Version 26.0. Armonk, NY: IBM Corp.). The primary outcome will be tested using an independent samples *t*-test. To assess for any differences in VAS scores based on demographic data, independent *t*-tests will be utilized. To assess for normality of distributions in the sample's continuous demographic and clinical characteristics, z-scores will be formed by dividing skewness by the standard error of skewness. This is performed to ensure that parametric measures can be used for the two groups. A Fisher's exact test will be used to assess the lower dose for a difference in adverse effects. During analysis, it was determined that the pain reduction variables could be compared by age and body weight using Pearson correlations. Additionally, the pain reduction variables will be compared by gender, duration of pain (\leq 24 hours vs. $>$ 24 hours), and location of pain (back/neck vs. other locations and small vs. large joints) using independent *t*-tests.

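### The primary non-inferiority t-test ignores the pre-treatment VAS that every subject already supplies; adjusting for it would usually gain precision at almost no cost

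*Protocol*

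**What the plan says.** Protocol Section 11.1 defines the endpoint as a change score: "The primary outcome will be the difference in VAS from baseline to 30 minutes and from baseline to 60 minutes". Section 11.6 gives the test: "The hypothesis will be tested using the construction of one-sided confidence intervals or one-sided, two-sample equal-variance t-test with alpha of 0.05". The SAP is shorter: "The primary outcome will be tested using an independent samples" t-test. No covariate is named in any of these places.

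The form's prompt in Section 11.1 asks the authors to "Describe how confounding variables will be controlled in the data analysis"; the answer names no variable. The SAP does relate pain reduction to patient characteristics: "During analysis, it was determined that the pain reduction variables could be compared by age and body weight using Pearson correlations", and "Additionally, the pain reduction variables will be compared by gender, duration of pain" and location. These are separate tests that do not adjust the dose comparison, and pre-treatment VAS is not among them.

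Section 10.1 (Medication Administration) has the pre-treatment VAS marked while the drug is being prepared, so the covariate exists for everyone and is needed to form the change score.

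Section 11.5 sets the margin at -13 mm, the true difference at 0, the SD at 27, and 55 evaluable subjects per arm for 80% power, raised to 61 for 10% dropout. It describes the comparison this way: "In this study, we assume that we are comparing the mean VAS between the 2 Groups". Section 10.2 speaks of change: "This study will use a previously validated measure of a 13 mm change in VAS".

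**The concern.** Subtracting baseline is not the same as adjusting for it. A change score fixes the slope of follow-up VAS on baseline VAS at 1. Analysis of covariance (ANCOVA) estimates that slope from the data. Unless the true slope is 1, the change score carries avoidable noise.

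This matters because the verdict turns on whether a one-sided confidence limit stays within 13 mm, so its width is decisive. There is little slack: 61 × 0.9 = 54.9 per arm, just the 55 required. A wider limit than necessary raises the chance that a truly non-inferior lower dose fails to be shown so.

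**Working it through.** **Inputs from the documents.** One-sided alpha 0.05, margin 13 mm, true difference 0, SD 27 mm, 55 evaluable per arm (Section 11.5). **Not in the documents, so assumed:** the baseline SD (SD0), the follow-up SD (SD1) and their within-arm correlation r.

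**Step 1: reproduce the plan.** The standard error is 27 × √(2/55) = 5.149 mm, and the noncentrality is 13 / 5.149 = 2.525. With 108 df, the noncentral t gives power 80.6% (54 per arm just misses 80%), so 55 per arm reproduces. The one-sided half-width is 1.659 × 5.149 = 8.54 mm, so the largest observed shortfall that still passes is 13 − 8.54 = 4.46 mm.

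**Step 2: compare the variances.**
- Change score: SD0² + SD1² − 2·r·SD0·SD1
- ANCOVA residual: SD1²·(1 − r²)
- Difference: SD0² − 2·r·SD0·SD1 + r²·SD1² = (SD0 − r·SD1)²

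A square cannot be negative, so ANCOVA never has the larger residual variance. The gain is nil when r = SD0/SD1, that is, when the slope is 1. The costs are one df (107 instead of 108) and an average variance inflation of about 1 + 1/106 = 1.009 for chance covariate imbalance. With nil gain and both costs, power is 80.3% against 80.6%.

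**Step 3: 27 mm is the SD of change, SD0 = SD1.** The variance ratio is (1 − r²) / [2(1 − r)] = (1 + r)/2.

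| r | ANCOVA SD (mm) | Variance saved | Power, 55 per arm | Largest passing shortfall (mm) | n per arm for 80% |
|---|---|---|---|---|---|
| unadjusted | 27.0 | – | 80.6% | 4.5 | 55 |
| 0.3 | 21.8 | 35% | 92.9% | 6.1 | 36 |
| 0.5 | 23.4 | 25% | 89.5% | 5.6 | 41 |
| 0.7 | 24.9 | 15% | 85.9% | 5.1 | 47 |

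These figures include the lost df but not the 1.009 factor. With it, power is 92.7, 89.2 and 85.6%.

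**Step 4: 27 mm is the SD of change, SD0:SD1 = 20:27.** The 20 mm entry floor (Section 12.5) may make baseline less variable than follow-up. The proportion of variance saved is (SD0 − r·SD1)² divided by the change-score variance.

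| r | Variance saved | Power |
|---|---|---|
| 0.3 | 17.6% | 86.8% |
| 0.4 | 12.1% | 84.9% |
| 0.5 | 7.2% | 83.1% |
| 0.6 | 3.0% | 81.7% |
| 0.7 | 0.3% | 80.7% |

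With the 1.009 factor the range is 86.6% to 80.4%; the last figure is marginally below the unadjusted 80.6%.

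**Step 5: 27 mm is a single-time SD.** With equal SDs, the change SD is 27·√[2(1 − r)] and the ANCOVA SD is 27·√(1 − r²). The last column gives the planned test with SD0 = 20 and SD1 = 27; ANCOVA power is the same in both settings because it depends only on SD1 and r.

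| r | Change SD, equal SDs (mm) | Planned test, equal SDs | ANCOVA SD (mm) | ANCOVA power | Planned test, SDs 20 and 27 |
|---|---|---|---|---|---|
| 0.2 | 34.2 | 63.3% | 26.5 | 82.0% | 72.5% |
| 0.3 | 31.9 | 68.3% | 25.8 | 83.8% | 77.1% |
| 0.4 | 29.6 | 74.1% | 24.7 | 86.3% | 82.2% |
| 0.5 | 27.0 | 80.6% | 23.4 | 89.5% | 87.4% |
| 0.6 | 24.1 | 87.7% | 21.6 | 93.2% | 92.6% |
| 0.7 | 20.9 | 94.5% | 19.3 | 96.9% | 96.9% |

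**The case against.** The strongest reply is that nothing here is an error. The planned test is legitimate, its sample size reproduces, and a change score already uses the baseline. The gain rests on quantities the documents do not supply and can shrink to nothing, so the most favourable figure (92.9%) should not be read as the expected benefit. All of that stands, and it is why this is a recommendation rather than a defect. It does not remove the asymmetry: the downside is about 0.3 points of power, while the upside is several points over much of the plausible range.

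Second, the form's question about confounders is weak support, since randomisation deals with baseline confounding in expectation. Agreed; the argument here is precision and does not depend on that prompt.

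Third, pre-treatment VAS is marked after assignment, on a form whose study number shows the dose. That is true, but it affects the planned change score as well.

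Fourth, adjustment leaves other matters open: the SAP's silence on margin and sidedness, the lack of a decision rule for two primary time points, and removals after randomisation. These are separate issues. The model proposed here supplies a margin and a one-sided limit but does not repair the others.

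Finally, the SAP's wording suggests that analysis may have begun, in which case changing the primary model could look results-driven. This objection has force and determines the form of the fix.

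**Conclusion.** The concern holds as a missed efficiency. The primary comparison is unadjusted, the covariate is already collected, and adjustment cannot increase residual variance. If 27 mm is the SD of change, power at 55 per arm rises from 80.6% to between 85.9% and 92.9% with equal SDs, or to between 80.7% and 86.8% with a 20:27 ratio, for r from 0.3 to 0.7. If 27 mm is a single-time SD, the gain runs from about 19 points (equal SDs, r = 0.2) to nil (SDs 20 and 27, r = 0.7). All values of r and the SD ratio are assumptions.

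None of this shows that the trial is underpowered or its planned test biased. The margin and the 13 mm change criterion suggest that Section 11.5 means mean reduction, but the plan does not say which SD 27 mm is, and ANCOVA does not settle that.

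**What to change.** - In the SAP, make the primary analysis a linear model of VAS reduction on arm with pre-treatment VAS as covariate, fitted separately at 30 and at 60 minutes. Compare the one-sided 95% lower limit of the adjusted difference (15 mg minus 60 mg) with -13 mm.
- Keep the unadjusted t-test as a sensitivity analysis.
- Keep the planned sample size and treat any gain as extra power.
- State in Section 11.5 whether 27 mm is the SD of change or of a single-time score.
- If results by arm have already been seen, leave the t-test as primary and report the adjusted model as a labelled post hoc sensitivity analysis. It then adds no power to the primary verdict.

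The cost is one SAP sentence and a standard procedure in the software already named, with no new data or subjects.
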